7.2 Study case report forms (CRFs)

Electronic case report forms will be completed for each participant to capture study specific information. Data will be collected through electronic case report forms designed for this study and through secure IT/connectivity solutions designed for the transmission of testing results.

7.3 Process evaluation

Process outcomes will be tracked via our central point-of-care test database that captures deidentified individual patient and quality management electronic test results from the GeneXpert

platform (includes valid/invalid results). Using connectivity software, data are captured in real-time, cleaned and analysed to generate process outcomes, displayed on our internal dashboard, and available for real-time reporting. We will evaluate the proportion of tests with an invalid/error/no result (usually <5% but an important indicator of problems with point-of-care testing procedures and prompt review of training). We record the numbers of staff trained (initial and refresher courses), and frequency/outcomes of quality assurance/competency testing.

8. Statistics

8.1 Primary outcome

The proportion of HCV RNA detectable participants who initiate HCV treatment within 12 weeks of HCV RNA testing.

8.2 Sample size

Overall, 40,000 point-of-care HCV tests will be performed in different settings as part of the Australian National HCV Point-of-care Testing Program. It is estimated that the HCV prevalence will be 15% (n=6,000 people who are HCV RNA detectable) and the treatment uptake following testing will be 65% (n=3,900). Under these assumptions, the 95% confidence intervals around the estimate for HCV treatment uptake will be 64.0%-66.0% and for HCV RNA prevalence will be 14.7%-15.4%. For analyses evaluating factors associated with HCV treatment uptake, we will have 90% power to detect an odds ratio of 1.20 or greater ($\alpha=0.05$) for a variable that is 50% prevalent (i.e. recent injecting drug use).

Analysis will follow the STROBE guidelines for observational studies. The analysis of the primary outcome will occur when all patients have completed 12 weeks of follow-up (from enrolment) or have been permanently lost to follow-up. Participant flow will be summarised, showing the numbers of participants included. The primary endpoint will be the proportion of participants who initiate HCV treatment within 12 weeks of HCV RNA testing. The secondary endpoints will be:

- Proportion of people who accept point-of-care testing among those offered testing.
- Proportion of people who are HCV RNA detectable among people tested.
- Time to HCV treatment uptake following finger-stick point-of-care HCV antibody testing with reflex HCV RNA testing among people who receive treatment.
- Proportion of HCV RNA detectable participants who initiate HCV DAA treatment at 12 months (52 weeks) following enrolment.
- Proportion of participants who complete HCV direct-acting antiviral (DAA) treatment.
- Proportion of participants who achieve an SVR (defined as HCV RNA below the lower limit of quantitation at post treatment week 12).
- To evaluate the proportion of HCV RNA detectable participants who are HCV RNA negative at 12 months (52 weeks) following finger-stick point-of-care HCV antibody testing with reflex HCV RNA testing.
- Cost-effectiveness of different testing strategies.

Participant characteristics at baseline will be summarised. Factors hypothesised to be associated with treatment initiation within 12 weeks of testing will be determined *a priori* and will include age, gender, Aboriginal and Torres Strait Islander status, and geography. Logistic regression will be used to assess factors associated with treatment initiation. Secondary analyses will be performed on these outcomes with stratified analyses performed where possible.

A detailed statistical analysis plan will be developed towards completion of the study, and prior to analyses being performed.

9. Data collection, source documents and record retention

The Principal Investigator and the institution where the study will be conducted will permit study-related monitoring, audits and ethics committee review providing direct access to source documents. Flinders University, NSW Pathology (NSW study sites) and Cepheid may also request to conduct an audit or inspection at sites. Prior to this they would seek permission from the site to access study related records physically at site.

Data will be collected on study specific electronic or paper copy case record forms. The Principal Investigator is responsible for ensuring the data collected are complete, accurate and recorded in a timely manner.

Data will be collected in a de-identified format and submitted to the Kirby. All data will be stored in the secure study database, RedCap, and will be kept on a secure password protected server hosted by UNSW Sydney, until its destruction. Only approved site staff and study staff, will have access to this data. Site staff will be responsible for collecting and entering the data for their site, and will only have access to the study data collected at their own site.

De-identified data collected from this research project may be used in future research projects following separate review and approval from a Human Research Ethics Committee (HREC).

The informed consent forms will be stored at site level according to the site's local process, and in accordance with ICH-GCP guidelines. Archiving and subsequent secure destruction of the informed consent forms and other study specific documents at site level are the responsibility of the Principal Investigator. When the period for archiving has elapsed, sites will be notified by the Sponsor, UNSW Sydney, to securely destroy the documents in accordance with ICH-GCP guidelines.

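### The 95% confidence interval given for treatment uptake (64.0%-66.0%) does not follow from 3,900 of 6,000; those inputs give 63.8%-66.2%

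*Protocol*

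**What the plan says.** Section 8.2 (Sample size) sets out the planning assumptions in order:

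- Volume: "Overall, 40,000 point-of-care HCV tests will be performed in different settings".
- Infection: "It is estimated that the HCV prevalence will be 15% (n=6,000 people who are HCV RNA detectable").
- Uptake: "the treatment uptake following testing will be 65% (n=3,900").

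From these it states that "the 95% confidence intervals around the estimate for HCV treatment uptake will be 64.0%-66.0" per cent and, in the same sentence, "for HCV RNA prevalence will be 14.7%-15.4" per cent. The synopsis, under Statistics, repeats the same assumptions and both intervals.

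The proportion concerned is the primary outcome, defined in section 8.1 as "The proportion of HCV RNA detectable participants who initiate HCV treatment within 12 weeks of HCV RNA testing". The protocol names no interval method, design effect, finite-population correction or other denominator.

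**The concern.** The uptake interval is printed as a direct consequence of the assumptions just before it, but a half-width of exactly 1.0 point looks too small for a proportion of 65% in 6,000 people. This is the only precision figure the protocol gives for its primary outcome. The primary hypothesis in section 2 is that uptake exceeds 65%, so precision close to 65% is what a reader will look for. If the interval is wrong, the protocol claims slightly more precision than its own numbers support. Because the figure stands in two places, it could also be carried into the later analysis plan or a report.

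**Working it through.** **Inputs**, all from section 8.2 and repeated in the synopsis: 40,000 tests; 15% RNA detectable, n = 6,000; 65% uptake, n = 3,900; confidence level 95%.

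**Step 1. Try to reproduce the printed uptake interval.**

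SE = sqrt(p(1 − p)/n) = sqrt(0.65 × 0.35 / 6,000) = 0.006158, or 0.616 points.

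Half-width = 1.96 × 0.616 = 1.207 points.

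Interval = 65 ± 1.207 = 63.79% to 66.21%, which prints as 63.8%-66.2%. The printed 64.0%-66.0% is not reproduced.

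**Step 2. See whether another 95% method gives the printed limits.**

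| Method (3,900/6,000, 95%) | Lower % | Upper % |
|---|---|---|
| Wald | 63.793 | 66.207 |
| Wilson | 63.784 | 66.197 |
| Agresti-Coull | 63.784 | 66.197 |
| Jeffreys | 63.786 | 66.199 |
| Exact (Clopper-Pearson) | 63.778 | 66.208 |
| Wald with continuity correction | 63.785 | 66.215 |

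Every row prints as 63.8%-66.2%, so the choice of method does not explain the difference.

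**Step 3. Cross-check the companion interval.** For prevalence, 6,000/40,000 at 95%, Wilson gives 14.653%-15.353% and exact gives 14.651%-15.354%. Both print as the stated 14.7%-15.4%. (Wald gives 14.6501%-15.3499%, which prints as 14.7%-15.3%.) At 90% every method tried prints 14.7%-15.3%. The prevalence interval is therefore a genuine 95% interval to one decimal, and the uptake interval beside it is not.

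**Step 4. Ask what would give ±1.0 point.**

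- *A different denominator.* n = (1.96/0.01)² × 0.65 × 0.35, or about 8,740. Allowing the half-width to lie between 0.95 and 1.05 points, n runs from about 7,930 to 9,680. The protocol gives 6,000.
- *A finite-population correction.* With N = 40,000 the half-width is 1.11 points. With N = 128,000 (the number living with HCV in Australia in 2019, section 1) it is 1.18 points. Neither is 1.0.
- *A different confidence level.* 1.0/0.616 = 1.624 standard errors, a nominal level of 89.6%. A 90% Wald interval is 63.99%-66.01%, which prints as 64.0%-66.0%, but the text says 95%.
- *Rounding.* Limits of 63.8 and 66.2 rounded to whole per cent and then written with a trailing zero also give the printed figures.

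The protocol does not say how the figure was obtained, so the last two remain possible origins only.

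**Step 5. Size of the error.** Correct width 2 × 1.207 = 2.414 points; printed width 2.0 points; 2.0/2.414 = 0.829. The printed interval is about 17% too narrow, which in absolute terms is 0.2 points at each limit.

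**The case against.** The strongest reply concerns weight. A shift of 0.2 points at each end of an interval around 65% would change nobody's reading of the study. The 40,000 tests are presented as a programme volume, not derived from a target interval width. The power statement that follows does not inherit the error: with 6,000 people, a factor present in half of them and an odds ratio of 1.20, power is about 91% to 92%, in line with the stated 90%. All of this stands and keeps the point minor.

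A second reply is that the figure is merely rounded. That may be how it arose, but the limits are printed to one decimal, like the prevalence interval beside them, and at that precision they are wrong.

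A third reply is that 63.8%-66.2% is not the study's true precision either. It treats 6,000 as independent people, whereas section 8.2 counts tests, section 4 counts participants, section 5 allows repeat testing without new enrolment, and recruitment runs across many services. Positive correlation within sites would widen the interval. This is fair, but it moves further from the printed figure, and the protocol gives nothing with which to quantify it. It bears on how the correction is worded, not on whether one is needed.

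**Conclusion.** The concern holds. Under the protocol's own assumptions (3,900 of 6,000, independent observations, 95% level) the interval for treatment uptake is 63.8%-66.2%. The half-width is 1.21 points, where the protocol implies 1.0. The conclusion does not depend on the interval method and needs no outside figure. The slip is in the favourable direction and concerns the primary outcome, but its effect ends with that one statement. Minor.

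**What to change.** Replace 64.0%-66.0% with 63.8%-66.2% in section 8.2 and in the Statistics entry of the synopsis. Keep the existing qualification that the figure holds under the stated assumptions, so that it is not read as allowing for clustering or repeat tests. Leave the prevalence interval as it is. The cost is one figure corrected in two places, with no change to participant numbers, endpoints or analysis.

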5. To evaluate the proportion of HCV RNA positive participants who initiate HCV treatment at 12 months (52 weeks) following HCV RNA testing.
6. To evaluate the proportion of participants who complete HCV direct-acting antiviral (DAA) treatment following point-of-care HCV antibody testing with reflex HCV RNA testing in those who are HCV antibody detectable who received HCV treatment;
7. To evaluate the proportion of participants who achieve an SVR (defined as HCV RNA below the lower limit of quantitation at post treatment week 12) following point-of-care HCV antibody testing with reflex HCV RNA testing in those who are HCV antibody detectable who received HCV treatment.
8. To evaluate the proportion of participants who are HCV RNA negative at 12 months (52 weeks) following HCV RNA testing.
9. To evaluate the cost-effectiveness of this testing strategy.

4. Participant population

Participants will be included from settings that provide services to people with a risk factor for the acquisition of HCV infection, including drug treatment clinics, needle and syringe programs, prisons, mobile outreach services, community health services, mental health services, homelessness services, and other appropriate settings nationally. It is anticipated approximately 40,000 participants will be screened for HCV infection using point-of-care HCV testing.

Inclusion criteria

Participants are eligible for inclusion if the following criteria are met:

- a. Provide informed consent
- b. ≥ 18 years of age.

Exclusion criteria

- b. Is unable or unwilling to provide informed consent

5. Study design

This is an observational cohort study. Participants will attend a single visit where they will provide informed consent and receive point-of-care HCV testing. All other study procedures will comprise data collection only.

Participants will be offered treatment as standard of care. Participants who are HCV RNA detectable will also be linked to standard of care for any other clinical assessments and treatment

initiation, and local health staff may provide counselling and medical advice for these tests, and link participants with support services available in their state or territory.

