Participants who return to the same site at a later date and require further HCV testing (as standard practice or due to a risk factor) can do so through the study without having to consent and enrol again. There is no time restrictions for when participants can receive another test, this is dependent on the individual case.

6. Treatment of participants

No treatment will be prescribed as a part of this study.

7. Study procedures

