7.1 Visits and Procedures

All participants receiving HCV testing at the participating sites will be identified. Site staff will discuss the research study with participants, and written or verbal consent will be obtained. If written consent, the participant will date and sign the participant information sheet and consent form together with the date and signature of the person conducting the consent discussion. If verbal consent is utilised the person conducting the consent will sign the verbal consent form to confirm that the study has been explained to the participant and consent has been given. A copy of the signed participant information and consent form will then be offered to the participant. Participants will then undergo HCV point-of-care testing. Further study procedures will comprise data collection at Week 12 and Week 52 only.

For participants who have previously been told they have HCV infection, or for people who have previously received HCV treatment, testing will be performed using point-of-care HCV RNA testing via Xpert HCV Viral Load Fingerstick assay using the GeneXpert machine (results in one hour). For all other participants who have not previously been told they have HCV infection nor have previously received HCV treatment, testing will be performed using point-of-care HCV antibody testing (results within 20 minutes). If the result is HCV antibody positive, individuals will undergo reflex HCV RNA testing. Where possible, the HCV RNA test will be performed via Xpert HCV Viral Load Fingerstick assay using the GeneXpert machine. If not available, HCV RNA testing will be performed via other standard of care methods.

The following participant information will be collected as part of this study, from the participating sites existing medical records available at the site, by site staff:

- Name code
- Aboriginal and Torres Strait Islander status
- Gender
- Age
- Medical Record Number
- HCV testing and status

Additional data collection for HCV RNA positive patients only:

- Previous HCV treatment
- HIV testing and status
- HBV testing and status
- HCV treatment regimen prescribed
- HCV treatment proposed duration
- HCV treatment start and end date
- Treatment completion (including reasons for not completing treatment)
- Treatment outcome (including reasons for not responding to treatment)

Additionally, a record of the overall number of patients who declined an HCV RNA test will be obtained from sites that record this data.

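### The primary analysis is triggered 12 weeks after enrolment while the primary outcome runs 12 weeks from the HCV RNA test, so the trigger does not guarantee a closed window where the RNA test comes after enrolment

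*Protocol*

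**What the plan says.** Protocol 8.1 defines the primary outcome as "The proportion of HCV RNA detectable participants who initiate HCV treatment within 12 weeks of HCV RNA testing". The clock starts at the RNA test, and the primary objective in section 3 uses the same anchor.

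Protocol 8.2 and the Statistics row of the synopsis give the timing of the analysis: "The analysis of the primary outcome will occur when all patients have completed 12 weeks of follow-up (from enrolment"), with the alternative "or have been permanently lost to follow-up". This clock starts at enrolment.

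Three other provisions decide whether the clocks agree:

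- Section 5 sets the default path: "Participants will attend a single visit where they will provide informed consent and receive point-of-care HCV testing".
- Section 5 also says that people who come back to the same site for further testing "can do so through the study without having to consent and enrol again", and adds: "There is no time restrictions for when participants can receive another test".
- Section 7.1 prefers the on-site assay for the RNA test, but allows for its absence: "If not available, HCV RNA testing will be performed via other standard of care methods". It sets no same-day requirement for that route.

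**The concern.** An analysis trigger should ensure that everyone counted in the outcome has had the full time in which the outcome can occur. Here it ensures this only if the RNA test is on the day of enrolment. A participant whose RNA test falls after the last enrolment date has, at the earliest permitted analysis, less than 12 weeks behind that test. If that participant is in the denominator and starts treatment later but still within the window, the analysis records a non-initiation.

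Miscounting of this kind can only lower the estimate. That matters somewhat because the hypothesis in section 2 is uptake above 65%, the planning value in 8.2 is 65% itself, and the planned interval is narrow.

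**Working it through.** **Reference precision.** Protocol 8.2 assumes 6,000 RNA-detectable people and 65% uptake, and states a 95% interval of 64.0% to 66.0%.

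- Standard error = √(0.65 × 0.35 / 6,000) = 0.616 points.
- 95% half-width = 1.96 × 0.616 = 1.21 points, giving 63.8% to 66.2%. Wilson and Clopper-Pearson intervals agree to one decimal.

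The stated interval does not reproduce; it matches a 90% interval (63.99% to 66.01%). That is a separate matter. The yardstick used below is 1.2 points.

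**Default path.** Consent and testing share one visit (section 5). Antibody results come within 20 minutes and RNA results in one hour (7.1). The gap between enrolment and RNA test is zero, so the bias is zero.

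**General formula where the RNA test is later.**

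Shortfall = 65% × (share of RNA-detectable participants with an open window at the cut) × (fraction of their 12-week starts not yet seen).

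The document gives neither of the last two terms, so both are assumptions. The formula also assumes that these participants are counted as non-initiators.

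**Route 1: reflex RNA test by another method.** Assume even accrual over 104 weeks, 20% of RNA-detectable participants tested with a lag of L weeks, and treatment starts spread evenly over 12 weeks. Only those enrolled in the last L weeks of accrual have an open window, and on average L/2 of their 12 weeks is unobserved.

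| Lag L | Share open = 0.20 × L/104 | Fraction unseen = (L/2)/12 | Shortfall (points) | Shortfall if all their starts are missed (points) |
|---|---|---|---|---|
| 2 weeks | 0.38% | 0.083 | 0.02 | 0.25 |
| 4 weeks | 0.77% | 0.167 | 0.08 | 0.50 |

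**Route 2: retest without new enrolment.** Let s be the share of RNA-detectable participants whose qualifying RNA test falls between the last enrolment and the cut, with test dates even over those 12 weeks. A start at week t after the test is then missed with probability t/12, so the fraction unseen is the mean start time divided by 12.

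- Even starts: 6/12 = 0.50.
- Front-loaded starts (exponential, scale 3 weeks, truncated at 12): mean about 2.8 weeks, 2.8/12 ≈ 0.23.

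| Assumed s | Even starts: shortfall (points), reading | Front-loaded starts: shortfall (points), reading |
|---|---|---|
| 1% | 65 × 0.01 × 0.50 = 0.33, reads 64.7% | 65 × 0.01 × 0.23 = 0.15, reads 64.9% (64.85%) |
| 5% | 65 × 0.05 × 0.50 = 1.63, reads 63.4% | 65 × 0.05 × 0.23 = 0.75, reads 64.25% |

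**Break-even.** To move the estimate by a full half-width with half the starts unseen, s must be 1.207 / (65 × 0.50) = 3.7%. With all starts unseen it must be 1.207 / 65 = 1.9%. Whether retests in the last 12 weeks reach that level cannot be told from the document.

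**The case against.** The strongest reply is that this is loose wording and not a design fault. Enrolment and testing are one time point on the planned path, and the assessment schedule puts consent and testing in a single column. Section 8.2 says when the analysis will occur. It does not say that an open window counts as non-initiation, nor that a retest brings someone into the primary denominator. The 6,000 are described as people; if the enrolment test is the qualifying one, retests never touch the primary outcome. Section 8 promises a detailed analysis plan before any analysis, which could settle these rules. Treatment start dates are collected and uptake is reviewed again at Week 52, so late-recorded starts could be recovered.

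Most of this stands, and it limits the point. A reader might infer from the two anchors that the primary analysis is generally run too early and that reported uptake is therefore biased low. The documents do not support that. The default path carries no bias, and the remaining bias needs three things that the protocol leaves unstated: a material retest rate, retests in the primary denominator, and open windows counted as failures.

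Two parts do not stand. The trigger is not left to the analysis plan: the protocol fixes it in two places with an explicit anchor that differs from the outcome's, so an analysis plan that corrected it would depart from the protocol. Recovery at Week 52 would come after the primary analysis, and no re-run is specified. Retests are also recorded, since section 10.1 asks for a case report form after each participant test, and nothing excludes them from the denominator.

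**Conclusion.** The point holds as a minor inconsistency. The outcome clock and the analysis trigger have different anchors, and the protocol's own provisions let them separate, so the trigger as written does not guarantee that every 12-week window has closed.

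For late reflex tests the consequence is negligible under the assumptions shown. For retests the size is unknown. Of the four scenarios at an assumed 1% to 5%, only the most extreme (5% with even starts, 1.63 points) exceeds the 1.2-point half-width. The downward direction is certain only if participants with open windows are kept and counted as non-initiators.

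**What to change.** In section 8.2 and the synopsis, replace the enrolment anchor with one of these:

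- Run the primary analysis when every HCV RNA detectable participant in the primary denominator has completed 12 weeks from the qualifying HCV RNA test and the Week 12 record review for that test is done.
- Include only qualifying RNA tests dated at least 12 weeks before the data cut.

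With either, state which test qualifies for a retested participant, for example the first HCV RNA detectable test in the study. That definition alone is not enough: someone first found detectable on a late retest would still have an open window under the present trigger.

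The cost is a wording change in two places. The first option brings a short delay, and needs a last date for qualifying tests if retesting continues. The second avoids the delay but drops a few late tests from the denominator.

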	
Secondary Objectives
 
 1. To evaluate the proportion of people who accept point-of-care testing among those offered testing. 2. To evaluate the prevalence of current HCV infection (HCV RNA quantifiable) among people tested. 3. To evaluate the HCV antibody prevalence among people tested. 4. To evaluate the time to treatment uptake among people receiving point-of-care HCV antibody testing with reflex HCV RNA testing in those who are HCV antibody detectable who received HCV treatment; 5. To evaluate the proportion of HCV RNA positive participants who initiate HCV treatment at 12 months (52 weeks) following HCV RNA testing. 6. To evaluate the proportion of participants who complete HCV direct-acting antiviral (DAA) treatment following point-of-care HCV antibody testing with reflex HCV RNA testing in those who are HCV antibody detectable who received HCV treatment; 7. To evaluate the proportion of participants who achieve an SVR (defined as HCV RNA below the lower limit of quantitation at post treatment week 12) following point-of-care HCV antibody testing with reflex HCV RNA testing in those who are HCV antibody detectable who received HCV treatment. 8. To evaluate the proportion of participants who are HCV RNA negative at 12 months (52 weeks) following HCV RNA testing. 9. To evaluate the cost-effectiveness of this testing strategy.

Participant population
	
Participants will be included from settings that provide services to people with a risk factor for the acquisition of HCV infection, including drug treatment clinics, needle and syringe programs, prisons, mobile outreach services, community health services, mental health services, homelessness services, and other appropriate settings nationally. It is anticipated that approximately 40,000 participants will be screened for HCV infection using point-of-care HCV testing.
 
Inclusion criteria

	
Participants are eligible for inclusion if the following criteria are met:
 
 a. Provide informed consent b. ≥ 18 years of age. 
Exclusion criteria
 
 a. Is unable or unwilling to provide informed consent
Study design	
This is an observational cohort study. Participants will attend a single visit where they will provide informed consent and receive point-of-care HCV testing. All other study procedures will comprise data collection only.

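### Secondary objective 5 times 52-week treatment uptake from HCV RNA testing, but its endpoint in section 8.2 times it from enrolment; the two differ when the RNA test falls after enrolment

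*Protocol*

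**What the plan says.** Secondary objective 5 appears in the same words in the Synopsis and in section 3: "To evaluate the proportion of HCV RNA positive participants who initiate HCV treatment at 12 months (52 weeks) following HCV RNA testing". The corresponding secondary endpoint in section 8.2 reads: "Proportion of HCV RNA detectable participants who initiate HCV DAA treatment at 12 months (52 weeks) following enrolment".

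Four other places bear on whether the two time origins are the same date.

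- Section 5 (Study design) describes one visit: "Participants will attend a single visit where they will provide informed consent and receive point-of-care HCV testing".
- Section 5 also covers people who come back to the same site for another HCV test. They "can do so through the study without having to consent and enrol again", and "There is no time restrictions for when participants can receive another test".
- Section 7.1 provides for RNA testing by other standard-of-care methods where the GeneXpert assay is not available. It then limits follow-up: "Further study procedures will comprise data collection at Week 12 and Week 52 only". It does not say from which date those weeks are counted.
- Section 8.1 times the primary outcome from HCV RNA testing. Section 8.2 times the primary analysis by 12 weeks of follow-up counted from enrolment.

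**The concern.** An objective and its own endpoint should share a time origin. Here they do not, and both statements are current text. No sentence equates the enrolment date with the RNA test date, and none limits the endpoint to tests done at the enrolment visit.

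If infections first found after enrolment are counted, following section 8.2 as written shortens their window, or removes it altogether from week 52 on. The reported 52-week uptake then depends on which section the analyst follows. The two uptake endpoints can also disagree about one person. Someone RNA-positive at week 46 after enrolment and treated at week 54 started 8 weeks after the test, so meets the primary outcome, yet is untreated on the 52-week enrolment clock. (This presumes that a record review takes place late enough to see the week-54 start.)

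The same slip affects when the primary analysis is run. Twelve weeks after enrolment is not twelve weeks after an RNA test done later, so a recent late test could enter the primary analysis before its own 12 weeks are complete.

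**Working it through.** **Step 1: where the clocks agree.** For an RNA test at the enrolment visit, the gap between enrolment and test is t = 0 and the two wordings give the same answer.

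**Step 2: where they part.** For an RNA test t weeks after enrolment, the enrolment clock leaves max(0, 52 − t) weeks:

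- t = 20: 32 weeks
- t = 40: 12 weeks
- t = 46: 6 weeks
- t ≥ 52: none

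The RNA-test clock always leaves 52. The enrolment clock can therefore only lower uptake.

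**Step 3: inputs for a size.** From section 8.2: 6,000 RNA-detectable participants and 65% uptake (3,900). That 65% is not tied to 52 weeks. The protocol gives no retest rate, no retest timing and no delay for RNA tests done by other methods. Everything below is illustration by assumption.

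As a yardstick I use the 95% half-width: 1.96 × √(0.65 × 0.35 / 6,000) = 1.21 points, that is 63.8%–66.2%. The protocol prints 64.0%–66.0%, a half-width of 1.0. That is a separate matter, but the yardstick affects the break-even figures, so both are shown.

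**Step 4: base case.** Assume 65% uptake, all of it within 12 weeks of the test. The fraction captured with s weeks left is F(s) = s/12 (linear) or (1 − e^(−0.0875s))/0.65 (constant hazard), with F = 1 for s ≥ 12 and F = 0 for s ≤ 0. Mean capture c when t is spread evenly:

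- Weeks 0–52: linear (40 + 6)/52 = 0.885; constant hazard (40 + 7.03)/52 = 0.904.
- Weeks 0–104: 46/104 = 0.442; 47.03/104 = 0.452.

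If a share f of RNA-positives is affected, reported uptake = 65 × (1 − f(1 − c)). The bias equals the half-width at f = half-width / (65(1 − c)).

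| Late tests fall in | f = 1% | f = 5% | f = 10% | Break-even f (half-width 1.21) | Break-even f (half-width 1.0) |
|---|---|---|---|---|---|
| Weeks 0–52 | 64.92–64.94 | 64.62–64.69 | 64.25–64.38 | 16.1%–19.4% (966–1,166 people) | 13.3%–16.1% |
| Weeks 0–104 | 64.64 | 63.19–63.22 | 61.38–61.44 | 3.3%–3.4% (200–203 people) | 2.8% |
| All after week 52 (c = 0) | 64.35 | 61.75 | 58.50 | 1.9% (111 people) | 1.5% |

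**Step 5: slower uptake, late tests over weeks 0–52.**

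- Uptake 65% at week 12, rising linearly to 75% at week 52. Mean counted uptake is (12 × 32.5 + 40 × 70)/52 = 61.35%, a loss of 13.65 points. The half-width is 1.96 × √(0.75 × 0.25 / 6,000) = 1.096, so break-even is 1.096/13.65 = 8.0%.
- Constant hazard reaching 65% only at week 52, rate −ln(0.35)/52. Mean counted uptake is 1 − 0.65/1.0498 = 38.1%, a loss of 26.9 points, so break-even is 1.21/26.9 = 4.5%. But this curve puts 12-week uptake at 1 − e^(−1.0498 × 12/52) = 21.5%, far below the protocol's hypothesis of more than 65%, so it does not fit the plan's own expectations.

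**The case against.** The strongest reply is that the design makes enrolment and testing one event: a single visit, testing straight after consent, and one HCV testing column in the schedule in section 7.1. Section 8.2 uses enrolment twice, which suggests that the authors treat the terms as interchangeable. For people tested at that visit this is right, and they are probably most of the cohort.

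A second reply is that any effect requires later-detected infections to be counted, which the protocol neither says nor denies, and that handling repeat testers is ordinary material for a statistical analysis plan. The denominator question can indeed be left there. The time origin cannot: the protocol fixes two for one endpoint, and an analysis plan that follows one contradicts the other. Section 8.2 also defers the plan until towards completion of the study, when many Week 12 and Week 52 reviews will already have been done.

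A third reply is that the size is assumed throughout, and that in the base case with late tests over weeks 0–52, 10% affected moves the estimate by only 0.6 to 0.75 points. That stands.

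A reader might infer that the primary outcome is also ill-defined. The documents do not support that: it is timed from RNA testing throughout. Only the rule for when its analysis is run refers to enrolment.

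**Conclusion.** The mismatch is certain; its effect is conditional. Objective 5 and its endpoint use different time origins. The dates separate for retests under section 5 and possibly for RNA tests done by other methods under section 7.1, where the protocol states no delay.

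If those infections are counted, the enrolment clock lowers 52-week uptake. The size cannot be derived from the protocol. It is probably small if uptake is quick and late tests fall within the first year. It becomes noticeable if retests continue past week 52, which the protocol permits: in the weeks 0–104 case, about 200 affected people out of 6,000 shift the estimate by a full half-width. If only enrolment-visit tests are counted and RNA is tested at that visit, the wordings agree and nothing changes.

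It would go too far to say that 52-week uptake will be materially biased. That needs a retest rate the protocol does not give. Enrolment looks like the outlier, since the primary outcome and the 52-week RNA-negative endpoint in the same section are timed from testing. This is a minor to moderate point on a secondary endpoint.

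**What to change.** Make three edits to the protocol.

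1. In section 8.2, time the 52-week uptake endpoint from HCV RNA testing, as objective 5 does.
2. In section 8.2, count the 12 weeks that trigger the primary analysis from HCV RNA testing instead of from enrolment.
3. In section 7.1, state that the Week 12 and Week 52 record reviews run from the RNA test date.

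Whether infections found at a retest enter the denominator is the sponsor's choice. Whatever is chosen should apply equally to the 12-week and 52-week endpoints.

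The cost is small. Sample size and power do not change, and no new data items are needed: section 10.1 already has a case report form completed after each test, and section 7.1 already collects "HCV treatment start and end date". The downside is that a few late tests may require a slightly later data cut or be left out of the corresponding analysis. Reviews for later-detected infections, if these are counted, would also fall on their own dates.
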